# Aims for Phase II:

AIM 1. Compare F4C to a standard BIP in its efficacy to reduce FV by decreasing fathers' violent behavior, improve father-child interactions, and reduce child mental health symptoms. *Hypotheses.* Children of fathers who receive F4C (n=140), relative to BIP (n=140), will: (1a) experience less FV, (1b) have more positive father-child interactions, and (1c) have lower FV-related mental health symptoms (PTSD, internalizing/externalizing) at post treatment and 6- and 12-month follow-ups. The effects of both treatments on father and coparent mental health outcomes will also be examined (1d *exploratory*).

AIM 2. Identify and compare latent change profiles of therapeutic targets (RF, ER) in F4C and BIP fathers across the 18-week intervention. *Hypotheses*. Compared to BIP, more F4C fathers will show profiles of healthy change in therapeutic targets: (2a) masked coding of insession RF/ ER (i.e., increased RF and adaptive ER, decreased maladaptive ER), and (2b)

between-session self-reported RF/ ER (i.e., increased RF and adaptive ER, decreased maladaptive ER). F4C change profiles will reveal critical junctures in treatment that precipitate change, thereby serving to optimize timing/delivery of treatment components (2c, *exploratory*).

AIM 3. Examine the mediating role of therapeutic change targets (RF, ER) on child-related outcomes in F4C and BIP families. *Hypotheses*. Profiles of healthy change in RF and ER will mediate the treatment effect of F4C over BIP on: (3a) FV (3b) father-child interactions, and (3c) child mental health symptoms (PTSD, internalizing/externalizing) at post-treatment and at 6- and 12-month follow-ups.

2. **Background:** Describe the background information that led to the plan for this project. **Provide references** to support the expectation of obtaining useful scientific data.

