# Phase II Hypotheses:

**AIM 1 Hypotheses:** Children of fathers who receive F4C (n=180), relative to BIP (n=180), will: (1a) experience less family violence (FV), (1b) have more positive father-child interactions, and (1c) have lower FV-related mental health symptoms (PTSD, internalizing/externalizing) at post treatment and 6- and 12-month follow-ups. The effects of both treatments on father and coparent mental health outcomes will also be examined (1d exploratory). Hypotheses will be evaluated with the broad family of latent (growth) curve models (LGM), which estimate and compare trajectories of change for each case in the data. Group differences in changes will be tested in multiple group LGM models. Following analyses for our primary study hypotheses, we will examine whether child sex moderates child mental health outcomes between the F4C and BIP groups. Power. The planned sample size of 140 F4C and 140 BIP cases provides power of .91 to detect a small to moderate effect size (d = 0.12). The current study with 140 per group (even 126) per group assuming a conservative 30% attrition at follow-up) has sufficient power to determine small differences in changes between intervention groups on outcomes. LGM models for changes in latent rather than observed scores, for three or more waves of data, have the advantage of partialing out measurement error, and increasing the statistical power by at least 20%. See Statistical Design and Power Section for estimation method.

AIM 2 Hypotheses. Compared to BIP, more F4C fathers will show profiles of healthy change in therapeutic targets: (2a) masked coding of in-session RF/ ER (i.e., increased RF and adaptive ER, decreased maladaptive ER), and (2b) between-session self-reported RF/ ER (i.e., increased

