RF and adaptive ER, decreased maladaptive ER). F4C change profiles will reveal critical junctures in treatment that precipitate therapeutic change, thereby serving to optimize timing and delivery of treatment components (2c, exploratory). Group-based trajectory modeling from the family of latent growth mixture modeling (GMM) will be used first to examine the number of different trajectory groups and their profiles (e.g., stable low or high adaptative ER, gradual increase or decrease in RF level, initial increase, then stable RF level, rapid decrease followed by gradual decrease of maladaptive ER, etc.) during the intervention period, as well as determine whether F4C vs. BIP treatment conditions influence trajectory group membership. Initially, trajectories of each in-session and between-session therapeutic change target will be modeled separately. Because data are expected to have unequal measurement intervals, we will use a new feature in Mplus 8.8 for analyzing such data (i.e., *tinterval and dynamical SEM*), and explore a new Stata 17 module for irregular time spacing measurements (i.e., xtusreg).143 Subsequent models will simultaneously examine various combinations of these six related targets to identify appropriate group membership for the fathers. This therapeutic change grouping will be modeled as the mediating variable in subsequent mediation analyses. **Power.** Determining power in group-based trajectory modeling with unequal time gaps is complex and not well explored. Given that some applications have used the classical, similar analytic method, mixture LGM (with equal time gaps), to extract three classes with a sample size as low as 45,144 the current target sample size of 360 (or 252 with attrition) will be adequate to identify trajectory groups and test further differences between F4C and BIP groups.

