**AIM 3. Hypotheses.** Profiles of healthy change in RF and ER will mediate the treatment effect of F4C over BIP on: (3a) FV (3b) father-child interactions, and (3c) child mental health (PTSD, internalizing/externalizing) at post-treatment and at 6- and 12-month follow-ups. LGM mediation models will be used to evaluate the mediating effect of therapeutic change classes on the treatment impact on both the fathers' use of FV and children's outcomes. In particular, the baseline predictor will be father's randomly assigned intervention group: F4C vs. BIP, with father's therapeutic change in RF and ER trajectory groups from Aim 2 entered as a categorical mediator into a structural equation model framework to investigate the mechanisms of change in child outcomes at post-intervention and up to two subsequent follow-ups. **Power.** Power analyses for mediational LGM models with categorical mediators are rare. The specialized Mplus 8.8 SEM software however has been advancing the toolbox available for such complex models, and its recent capabilities promise to provide adequate statistical power with the proposed sample size.

4. **Participant Population:** Provide a detailed description of the types of participants who will be recruited into this study.

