# Phase II:

The target sample is 280 father-coparent dyads and their 9 months to 11 year-old children recruited from CPS-involved families referred to the Parent and Family Development Program (PFDP) at Yale or the UCONN Health Center Outpatient Psychiatry Clinic. Participants will be randomized to either F4C (n = 140) or BIP (n = 140) following a baseline assessment. Half of F4C and BIP families will be treated at Yale and half at UConn Health. Yale will serve families in

Greater New Haven region, while UConn Health will serve families in the Greater Hartford region. The two sites are approximately a 45-minute drive apart.

5. **Describe** how access to the population will be gained in the study.

Fathers referred to the Parent and Family Development Program or UCONN Health Center by the CT Department of Children and Families (DCF) or the community due to IPV or child maltreatment risk will be provided information about the study and asked to complete an initial brief screening if they are interested in participation. He will be told that his screening questionnaire (which will include demographic matching information such as age, ethnicity, city of residence, income, employment history, SA history etc.) will be reviewed and he will be contacted to set up further assessment sessions if he is found eligible by the PI based on our study's requirements. This will provide the opportunity for contact with the mother to conduct phone screening with her related to IPV and her willingness for their shared child to participate. Female co-parent and intimate partner contact information will be provided on the referral from DCF or community referral source so that fathers are not providing this information, and this will limit the possibility of coercion.

6. **Participant classification:** Check off all classifications of participants that will be specifically recruited for enrollment in the research project. Will participants who may require additional safeguards or other considerations be enrolled in the study? If so, identify the population of participants requiring special safeguards and provide a justification for their involvement.

🛛 Healthy	□Fetal material, placenta, or dead fetus
Prisoners	□Economically disadvantaged persons
🗆 Employees	□Pregnant women and/or fetuses
□ Females of childbearing pote	ential
	
 
Healthy
 
Prisoners
 
Employees
 
Females of childbearing pote
 

Click or tap here to enter text.

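### Aim 2 counts trajectory groups without a reference model that lets fathers vary, so finding more than one group would not show distinct change profiles, and the arm test on group membership can lose power

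*Combined protocol and SAP*

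**What the plan says.** All references are to the combined protocol and SAP. Under Aims for Phase II, Aim 2 is to "Identify and compare latent change profiles of therapeutic targets (RF, ER) in F4C and BIP fathers across the 18-week intervention". The hypothesis is "Compared to BIP, more F4C fathers will show profiles of healthy change in therapeutic targets", once for masked coding of sessions (2a) and once for self-report between sessions (2b).

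The Analytic Plan (Phase II Hypotheses, AIM 2) places the method, group-based trajectory modelling, in the growth mixture family. It "will be used first to examine the number of different trajectory groups and their profiles", and is also to "determine whether F4C vs. BIP treatment conditions influence trajectory group membership". Each target is modelled separately before the six are combined. Under AIM 3 the resulting groups are "entered as a categorical mediator into a structural equation model framework".

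The AIM 2 power paragraph cites a published application that extracted three classes from 45 cases and concludes that "the current target sample size of 360 (or 252 with attrition) will be adequate to identify trajectory groups". Under Participant Population, Phase II, the design is: "Participants will be randomized to either F4C (n = 140) or BIP (n = 140) following a baseline assessment". Section V, on how the sample size was derived, expects 196 complete cases.

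The plan gives no rule for choosing the number of groups, no within-group variance structure, no single-class random-effects model for RF or ER, and no direct F4C–BIP comparison of RF or ER change in Phase II. The latent growth models under AIM 1 are for the outcomes.

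**The concern.** In its usual form, group-based trajectory modelling treats every father in a group as having the same level and the same course, apart from independent noise at each occasion. Its one-group model therefore says that all fathers are alike. Rejecting it shows only that fathers differ. If RF and ER vary smoothly across fathers, the method cuts that spread into slices, and the slices may mainly reflect starting level. Some of the plan's own example profiles (stable at a low or a high level) differ in level and not in change.

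Three things are at stake. Aim 2 could present slices of ordinary spread as profiles of healthy change. The arm test on those slices may be a weak test of whether F4C changes RF and ER. Aim 3 would mediate through a grouping that carries limited information about change.

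**Working it through.** **Sample figures.** 360 × 0.70 = 252, so the arithmetic in AIM 2 is right, but its base is not the trial's: 140 + 140 = 280, and 280 × 0.70 = 196. AIM 2 states no power, effect size or class proportions, so there is no power figure to reproduce. That three classes could be extracted from 45 cases does not show that classes are real or that the arm test has power.

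**Occasions.** Table 1 lists the RF and ER self-reports weekly, and treatment lasts 18 weeks, so 2b has up to 18 occasions. Treatment Fidelity has 20% of sessions coded: 0.20 × 18 = 3.6, taken as 4 for 2a.

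**Models.**
- Group-based trajectory, usual form: y_it = β0k + β1k·t + e_it, with no father-specific terms within group k.
- Reference: y_it = (β0 + u0i) + (β1 + u1i)·t + e_it, one class, with u0 and u1 varying between fathers.
- Number of groups by BIC = −2 log L + p·log N.

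The documents give no RF or ER variances. Everything below assumes them, along with equal spacing and no missing data; Monte Carlo error is about ±6 to 9 points.

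**How many groups appear when no classes exist?** With identical fathers, BIC chose one group in 200 of 200 data sets. With fathers differing in level only (residual SD 1), ICC = s²/(s² + 1), and the reliability of a father's mean over T occasions is s²/(s² + 1/T):

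| Level SD | T | ICC | Reliability of mean | More than one group |
|---|---|---|---|---|
| 0.1 | 18 | 0.01 | 0.01/0.066 = 0.15 | 6% (N = 280) |
| 0.2 | 18 | 0.04 | 0.04/0.096 = 0.42 | 99.7% (N = 280) |
| 0.3 | 4 | 0.08 | 0.09/0.34 = 0.26 | 13% (N = 196), 28% (N = 280) |
| 0.5 | 4 | 0.20 | 0.25/0.50 = 0.50 | 99% (N = 196), 100% (N = 280) |

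Nobody in these data sets follows a different course. With one normal population whose level, slope and residual SDs are all 1, more than one group appeared in 100%. A mixture that allows within-class variance kept one class in 99–100% of normal data sets without classes.

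**What do the groups capture?** At level SD 0.7, slope SD 0.5 and residual SD 0.7, the groups explained 59–78% of the variance in level and 9–14% of the variance in change.

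**Power of the arm test.** Two-sided α = 0.05, 18 occasions on a 0–1 time scale, 140 per arm, arm difference 0.4 SD of true change. Closed-form check of the direct test with all SDs 1: Σ(t − t̄)² = 18 × 19/(12 × 17) = 1.676; SD of an estimated slope = √(1 + 1/1.676) = 1.264; standardised difference = 0.4/1.264 = 0.317; 0.317 × √70 = 2.65; power ≈ Φ(2.65 − 1.96) = 0.75, against 0.76 simulated.

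| Assumption (SDs 1 unless stated) | Membership test | Direct slope test |
|---|---|---|
| Level and slope uncorrelated | 0.20–0.27 | 0.76 |
| Correlation +0.4 | 0.22–0.26 | 0.82 |
| Correlation −0.4 | 0.39–0.47 | 0.70 |
| Slope SD 0.5 | 0.06–0.11 | 0.47 |
| Slope SD 2 | 0.42–0.54 | 0.82 |
| Level SD 0.3 | 0.56–0.62 | 0.72 |
| Two true change classes*, level SD 0.3 | 0.78 | 0.74 |
| Two true change classes*, level SD 1 | 0.27 | 0.74 |

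*Mean change 2 or 0, within-class slope SD 0.2; 40% against 60% of fathers in the changing class.

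At 98 per arm the first row becomes 0.16–0.23 against 0.52. The closed form gives Φ(0.317 × 7 − 1.96) = 0.60 for the direct test, so the simulated 0.52 is on the low side. With no arm effect, the membership test rejected in 2–6% of data sets at the 0.7/0.5/0.7 spread.

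**The case against.** **Zero within-group variance is not stated.** A reader might infer that the plan fixes it at zero. The documents do not say so: AIM 2 places the method in the growth mixture family and mentions dynamical structural equation models, so a version with random effects is not excluded. This stands. The defect is that the structure and the reference model are unspecified, and the named method's usual form has the problem.

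**The power loss depends on assumptions.** A reader might conclude that the arm test loses most of its power. Without RF or ER variances that cannot be asserted; the table includes rows with little or no loss. The slope comparison also favours a linear effect, whereas several of the plan's example profiles bend. In a simulation built the other way (F4C moved 20 percentage points of fathers from a flat course to one that rises then falls, 18 occasions, N = 280, level SD 0.2, residual SD 0.7), the membership test had power 0.84 and a linear-slope test 0.04; at level SD 0.7 it was 0.24 against 0.05. This stands, so replacing the groups by a linear slope is not justified.

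**The reference model can be fooled too.** With no classes, N = 196 and the 0.7/0.5/0.7 spread, BIC on a mixture with within-class variance chose more than one class in 2% of normal data sets with 4 occasions. That rose to 50% at skewness 1, 88% at skewness 1.5 and 100% with half of scores at a floor; with 18 occasions the four figures were 0%, 83%, 100% and 100%. The bootstrap test was not examined there. This stands and shapes the fix.

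**Limited consequence.** Aim 2 concerns mechanism, the critical-junctures part (2c) is labelled exploratory, and the primary outcome measure is the FSI-R.

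**Conclusion.** The point holds in this form. As written, a group count above one in Aim 2 would not be evidence of distinct change profiles. If the usual form is used, an ICC of about 0.04 suffices for several groups in the weekly data and about 0.2 in the coded sessions. A reader might infer that several profiles appear almost regardless of the data; with about 4 occasions and an ICC of 0.08 it was only 13–28%.

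The power loss is a possibility to plan for. It exceeded half when level variation was at least as large as variation in change and the two were uncorrelated or positively correlated, and was roughly a third to a half with negative correlation or larger slope variation. It was small when level variation was small, and absent when true change classes existed with little level variation; true classes with large level variation did not prevent it.

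A reader might also infer a risk of false treatment claims; the Type I error results do not support that. Independently of any simulation, the adequacy sentence rests on a precedent that does not address the arm test, and its 360/252 conflicts with 280/196. This should be corrected, but it does not threaten the primary comparison.

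**What to change.** 1. In AIM 2, state the within-class variance structure and the rule for choosing the number of groups.
2. For each RF and ER target, fit a single-class growth model with random intercept and slope, with curvature where the occasions allow, as the reference.
3. Call groups distinct profiles only if a mixture with within-class variance beats that reference on BIC and the bootstrap likelihood-ratio test, and the result survives a check for skewed or floored scores. Otherwise report them as descriptive groupings.
4. Add a direct F4C–BIP arm-by-time test of RF and ER change that allows curvature.
5. In AIM 3, add a sensitivity mediation using continuous change.
6. Replace the adequacy sentence with power for the arm-by-time contrast at 280 randomised and 196 completers, over a stated range of variances, and reconcile 360/252 with those figures.

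The cost is plan wording and a few extra models in Mplus, which is already planned. The profiles may have to be reported as descriptive only. The stricter rule can also miss real classes: with the two true change classes and level SD 1 above, BIC on the random-effects mixture found more than one class in 75% of data sets at 280 fathers and 60% at 196, against 98% at 280 with level SD 0.3.

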The RA will complete study assessments in person or via zoom with fathers, mothers and partners at baseline, immediately following intervention completion, at 6 and 12 month follow-ups. Each measure and timing of assessment are outlined in Table 1.

Table 1. Assessment	Rater	Baseline	Weekly During	Monthly During	Post- intervention	6& 12 Month- FU
Schedule			Intervention	Intervention		_
ir v Out comes						
Family Socialization Interview Revised (FSI-R)  – IPV module	Masked Coder	X			X	Х
Time-line follow-back for IPV (56, 57)	Father, Mother, Current Intimate Partner		Х			
Abusive Behavior Inventory (ABI)	Father, Mother, Current Intimate Partner	X			X	X
Court and Arrest Records	N/A	X				Х
Child Maltreatment and Parenting Outcomes						
Child Protective Services Records	N/A	X				X
Family Socialization Interview Revised (FSI-R)  – Parenting Risk module	Masked Coder	x			X	X
Timeline Followback-CM Risk	Father and Mother		х			
Conflict Tactics Scale-Parent Child	Father and Mother	x			x	X
Father-Child Free Play coded using Child Interactive Behavior Rating (CIB)+	Masked Coders	X			X	X (12 month only)
Children's Emotions Scale (RCES)	Mother and Father					
Brief Infant Toddler Social Emotional Assessment (BITSEA) Trauma Symptom Checklist for Young Children (TSCYC) or Trauma symptom checklist for children (TSCC) appropriate for child age	Mother and Father Children >7-Self Report	X			X	X
Kiddie Diagnostic Interview Schedule PTSD Module OR Diagnostic Infant and Preschool Assessment (DIPA) modified PTSD module	Mother and Father	X			x	x
Satisfaction Outcomes						
Client Satisfaction Questionnaire 8 (58)	Father				Х	
Intervention Targets (Mechanisms)						
Unified Protocol Skill Use Scale (UPSUS)122 and select items from the 28-item Brief COPE	Father		X			
Difficulties in Emotion Regulation Scale (59) DERS Short Form	Father	X	Х		x	Х
Reflective Functioning Questionnaire-8 (RFQ)(60)	Father	X	Х			
Parent Reflective Function Questionnaire (PRFQ) (61)	Father	X	X			
Intervention Process Variables						
Working Alliance Inventory (62)	Father and Clinician			Х		
CHANGE Coding	Trained Reliable Coders			Х		
Motivation to Change	Father			Х		

	1			1	1
Therapist Session Report Form	Clinician		x		
Other variables to classify the sample					
STRESS Trauma History and PTSD Scale	Father	Х			
Alcohol Use Disorders identification Test (AUDIT) – Self report(66)	Father	Х			
Drug Abuse Screening Test- 10 (DAST- 10)(67)	Father	Х			

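### Aim 2's test of arm on RF/ER trajectory class names no baseline adjustment; adding the same-instrument baseline score for the self-report targets is a near-free gain in precision

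*Combined protocol and SAP*

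**What the plan says.** Section IV, Analytic Plan, Phase II Hypotheses, Aim 2 states the hypothesis as "Compared to BIP, more F4C fathers will show profiles of healthy change in therapeutic targets". Part 2a uses masked in-session coding and part 2b between-session self-report. Group-based trajectory modelling comes first, to find the number and form of the classes, "as well as determine whether F4C vs. BIP treatment conditions influence trajectory group membership". The text neither names a covariate for that test nor rules one out.

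The example classes mix level and shape: "stable low or high adaptative ER, gradual increase or decrease in RF level", followed by others that are mainly shapes. The resulting grouping becomes the Aim 3 mediator.

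Table 1 lists "Difficulties in Emotion Regulation Scale (59) DERS Short Form", the RFQ-8 and the PRFQ at baseline and weekly during the intervention. "CHANGE Coding" is listed only during the intervention, and the Unified Protocol Skill Use Scale (UPSUS) with Brief COPE items only weekly. The Phase II part of Participant Population places randomisation after the baseline assessment. The stratification variables named under Child Mental Health are residence with the child, protective order and substance use; RF and ER are not among them. The Preliminary Analysis paragraph plans to explore baseline differences between groups but states no adjustment.

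**The concern.** A class such as "stable low or high adaptative ER" sorts fathers by where they stand as well as by how they move. A father who enters treatment high will tend to land in a high class in either arm. That part of class membership cannot respond to treatment, and an unadjusted arm comparison treats it as noise.

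What is at stake is power: a greater chance of missing a true shift toward healthy profiles in Aim 2, and a less precise arm-to-mediator path in Aim 3. The covariate that would remove some of this noise is measured before randomisation and already collected. Aim 2 has little power to spare, since it gives no power figure and justifies its sample by a count larger than the enrolment target.

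**Working it through.** **The plan's own figure.** Aim 2 gives only a sample size: 360, or 252 after attrition. 360 × 0.70 = 252 reproduces. The Phase II target is 280, though, and 280 × 0.70 = 196 (98 per arm), the completer count given under Targeted Enrollment. I therefore used 140 and 98 per arm.

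**Assumptions, none of them in the documents.** Two-sided α = 0.05; share of fathers in the favourable class 0.30 (BIP) against 0.45 (F4C), or 0.40 against 0.55.

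**Unadjusted power by formula.** Power = Φ[(|p1 − p0| − 1.96·SE0) / SE1], with SE0 = √(2p̄(1 − p̄)/n) and SE1 = √([p0(1 − p0) + p1(1 − p1)]/n). For 0.30 against 0.45, p̄ = 0.375.
- n = 140: SE0 = 0.0579, SE1 = 0.0572; (0.15 − 0.1134)/0.0572 = 0.64; power 0.74.
- n = 98: SE0 = 0.0692, SE1 = 0.0683; (0.15 − 0.1356)/0.0683 = 0.21; power 0.58.

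**Effect of adjusting.** A father is in the favourable class if Φ⁻¹(p_arm) + ρB + √(1 − ρ²)e > 0, with B the baseline score and B and e standard normal. This fixes the class shares and lets ρ, the correlation of B with class propensity, vary. Each trial has a logistic Wald test of arm, without and with B (3,000 trials per cell). Cells show power unadjusted → adjusted.

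| ρ² (ρ) | 0.30 v 0.45, 140/arm | 0.30 v 0.45, 98/arm | 0.40 v 0.55, 140/arm | 0.40 v 0.55, 98/arm |
|---|---|---|---|---|
| 0 (0) | 0.744 → 0.744 | 0.584 → 0.590 | 0.716 → 0.717 | 0.564 → 0.561 |
| 0.10 (0.32) | 0.733 → 0.763 | 0.595 → 0.624 | 0.693 → 0.726 | 0.584 → 0.603 |
| 0.25 (0.50) | 0.736 → 0.810 | 0.579 → 0.661 | 0.696 → 0.778 | 0.586 → 0.628 |
| 0.50 (0.71) | 0.754 → 0.886 | 0.565 → 0.769 | 0.701 → 0.869 | 0.562 → 0.721 |

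The gain is nil at ρ = 0, about 2 to 3 points at 0.32, 4 to 8 at 0.50 and 13 to 20 at 0.71. A separate run with 40% favourable in BIP and an effect of 0.35 to 0.42 SD (1,500 replicates) gave 0 to 3 points at 0.3, 5 to 9 at 0.5 and 13 to 17 at 0.7. Pooled over both: 0 to 3, 4 to 9 and 13 to 20.

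**Check with fitted trajectory classes.** Simulated 18-week data, quadratic group-based models, modal class regressed on arm.
- Upper classes by final level counted as favourable, arm difference 0.4 SD, 3 or 4 classes, 150 trials per cell: power rose in all 12 cells. The largest rise was 0.35 to 0.55 (140/arm, 4 classes, slope SD 0.5); among the smallest was 0.21 to 0.24 (140/arm, 3 classes, slope SD 1.5). Class explained 44 to 80% of the variance in starting level.
- Class with the highest end value as healthy, effect 0.5 SD, start–end correlation 0.5, 500 replicates: 43% to 58% at 280 fathers, 29% to 44% at 196.
- Class with the largest increase as healthy, slope effect 0.5, 200 replicates per cell: gains mostly 4 to 18 points, but none in one cell (280 fathers, 4 classes, start–slope correlation −0.5: 32% both ways), where class correlated only 0.13 with baseline.

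**No treatment effect.** Rejection was 4.8% unadjusted and 6.2% adjusted (500 replicates, simulation SE about 1 point), and 5.3% and 7.3% in the 150-trial set (SE √(0.05 × 0.95/150) = 1.8 points). Both sets are compatible with 5%.

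**The case against.** Four points can be made for the plan as written.

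1. It is silent on covariates. A reader might infer that arm is specified as the only predictor; the text does not say so, and the Preliminary Analysis leaves room for looking at baseline variables. This stands. The defect is an omission in the stated test.

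2. A reader might infer that much of class membership is simply starting level. The documents do not support that. Hypotheses 2a and 2b concern change, most example classes are shapes, and no baseline correlation is given. The larger simulated gains come from defining healthy by final level, which builds level into the outcome. With healthy defined by increase, the gain usually remained but could vanish. This stands against any fixed size, not against the direction.

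3. Adjustment does not fit all of Aim 2. CHANGE coding (2a) and UPSUS/Brief COPE have no baseline value. The section on weekly and monthly measures names Parental Acceptance Rejection items, COPES and UPSUS as the treatment-target measures, whereas Table 1 also lists weekly DERS, RFQ-8 and PRFQ. A matching baseline score exists only if the latter are the modelled targets. This stands and limits the scope.

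4. A chance imbalance in baseline RF or ER might be read as bias. Randomisation makes it ordinary sampling error, which the unadjusted test already allows for; its null rejection was near 5%. This also stands.

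**Conclusion.** The point holds as a missed gain in precision. The arm-on-class test names no baseline adjustment, some of the example classes are level classes, and DERS, RFQ-8 and PRFQ are available before randomisation. The size cannot be fixed from the documents. Under the assumed class shares and α it is about 0 to 3 points of power at a correlation of 0.3, 4 to 9 at 0.5, 13 to 20 at 0.7, and nil if baseline and class are unrelated. The point applies directly to the self-report targets of 2b modelled with those three instruments, and to the combined grouping carried into Aim 3. For 2a and the skill-use items only proxy scores exist, and the gain is probably small. It is worth adopting because it costs almost nothing, not because Aim 2 would be invalid without it.

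**What to change.** Add to the Aim 2 analysis text:
- For each between-session target modelled with weekly DERS, RFQ-8 or PRFQ, regress class membership on arm plus the baseline score of the same instrument. Enter it after the number of classes is chosen, so that class enumeration is unaffected.
- Keep that baseline score out of the trajectory indicators, so that it is not both indicator and predictor.
- For the combined-target grouping used as the Aim 3 mediator, enter the baseline DERS, RFQ-8 and PRFQ scores.
- For CHANGE-coded targets and UPSUS/Brief COPE, treat these scores as optional proxies.
- Report unadjusted class proportions by arm beside the adjusted odds ratio, which is conditional on baseline.

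Also state which weekly measures are the modelled targets, so that Table 1 and the section on weekly and monthly measures agree. The cost is a few lines of text and no new data collection.
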